3.2. Blinding and Randomization

3.2.1. Randomization

There is no randomization in this study. All eligible patients will be enrolled and receive open-label andexanet treatment.

3.2.2. Blinding

This study will be open-label. However, the EAC will be blinded to all anti-fXa levels.

3.3. Duration of Study

The duration of the study for any individual patient will be up to 37 days.

There are 4 study periods. Study periods in the study for the respective cohorts are defined as follows:

- Screening Period: Day 1.
- Pre-surgical Assessment Period: Day 1.
- Treatment Period: Day 1.
 - Additional dosing during extended surgeries beyond initial andexanet dosing regimen (~ 2.5 hours) but no greater than a total of 6 hours (including both the initial regimen and the extended infusion).
 - Re-dosing (low dose bolus and infusion) may occur within 12 hours after completion of the first course of andexanet treatment if protocol specified criteria are met, at the investigators discretion. [refer to Section [6.2](#)]).
- Safety Follow-up Period: Days 1–30 + 7.

3.4. Discussion of Study Design, Including Choice of Control

3.4.1. Study Population

The study will enroll patients between the ages of 18 and 85 years who have recently taken an FXa inhibitor within 15 hours prior to start of surgery and who require urgent surgery for which reversal of anti-fXa activity is judged necessary.

If the time from last dose is unknown or greater than 15 hours, the patient may be enrolled provided a local anti-fXa activity level obtained within 2 hours prior to consent is > 100 ng/mL [> 0.5 IU/mL for enoxaparin]). In such cases the start of surgery must be no greater than 4 hours after the blood collection time for the local test.

Patients who are in need of urgent surgery within 12 hours of consent may be enrolled. Patients undergoing procedures for which the risk of clinically meaningful uncontrolled or unmanageable bleeding is low are not eligible. Patients with life-threatening bleeding (International Society on Thrombosis and Haemostasis [ISTH] definition, see Section 4.2) are also not eligible.

It is expected that eligible procedures may have varying degrees of tissue trauma but still have clinically relevant bleeding risk for which the reversal of FXa inhibition is judged necessary. For example, surgeries in a confined space (e.g., spinal cord decompression) can be considered to be at high bleeding risk even with relatively little tissue trauma, as opposed to an intra-abdominal surgery. Anticipated surgery types may include, but are not limited to, abdominal, thoracic, orthopedic, gynecological open and laparoscopic surgery. To ensure an adequate number of patients with certain key surgery types, abdominal surgeries (including both open and laparoscopic) and orthopedic surgeries will each comprise approximately 20% of the enrolled population. Patients undergoing only non-surgical invasive procedures (e.g., skin biopsies, lumbar puncture, cardiac catheterization, ERCP) will be excluded.

To align with previous studies of andexanet [4], the Efficacy Analysis Population for the study will only include patients whose central laboratory-determined anti-fXa activity is ≥ 75 ng/mL (≥ 0.25 IU/mL for patients receiving enoxaparin).

3.4.2. Rationale for the Study

The overall objective of the study is to gain direct insights regarding the efficacy and safety of andexanet in FXa-anticoagulated patients requiring urgent surgery. Additional information obtained from this study will include the adequacy and duration of andexanet dosing. The results of this study will be used to inform a subsequent randomized Phase 3 trial for registrational purposes.

3.4.2.1. Unmet Medical Need in Urgent Surgery

A substantial unmet medical need exists for patients taking FXa inhibitors who require rapid anticoagulant reversal prior to an urgent surgical procedure. In addition to the fact that approximately 1% of anticoagulated patients may require urgent surgery within 2 years of initiation [1, 2], management guidelines from the French Working Group of Perioperative Hemostasis suggest that 10% to 20% of treated patients may potentially undergo emergency surgery and invasive procedures during their lifetime [6]. Given the increasing adoption of FXa inhibitors worldwide, it is likely that progressively greater numbers of patients treated with FXa

inhibitors in need of urgent surgery will require reversal of anticoagulation, in addition to those with life-threatening or uncontrolled bleeding.

In general, it is well appreciated that urgent surgery is associated with an increased risk of complications as compared to elective surgeries. A recent study reported markedly increased rates of morbidity (12.3% vs. 6.7%) and mortality (2.3 vs. 0.4%) for urgent versus elective surgeries in 173,643 patients from a surgical database (NSQIP), of which 12% (> 20,000) were classified as urgent (non-elective/non-emergency) [7]. In the RE-LY study, the rate of major bleeding in dabigatran-treated patients was 17% for urgent surgery as compared to 3% in the larger study population. Perioperative rates of thromboembolism, major bleeding, and mortality were 5- to 10-fold higher in patients having an urgent rather than elective surgery/procedure. The need for urgent surgery was the strongest predictor of thromboembolism and major bleeding [8]. Similarly, data on 863 surgical patients treated with novel oral anticoagulants (NOACs) in the Dresden NOAC registry indicate an increase in major bleeding for patients with major versus minor surgery [9]. Finally, a sub-analysis of the Phase 3 ARISTOTLE trial showed a higher rate (4.9%) of major bleeding in apixaban-treated patients undergoing emergent surgery versus a rate of 2.1% in apixaban-treated patients in the overall study population [10, 11].

3.4.2.2. Management of Patients Taking FXa Inhibitors Requiring Urgent Surgery

There is currently no specific or approved treatment option for patients requiring reversal of FXa inhibition for urgent surgery. In general, if a patient is anticoagulated and requires surgery, the primary approach to managing this clinical scenario is to delay the procedure to facilitate elimination of the FXa inhibitor. Current practice is to weigh the risk of proceeding with the surgery, with the attendant prospect of hemorrhage, against the risk of delaying the procedure to achieve lower anti FXa activity levels. Inappropriate surgical delay could potentially result in serious or life-threatening clinical complications such as progressive contamination of the abdominal cavity (e.g., perforation of duodenal ulcer, perforated diverticulitis) or inflamed organ perforation (appendicitis). Postponement of treatment may also result in soft tissue infection progression, especially when diabetic comorbidity is present (e.g., abscess, necrotizing fasciitis). Delayed operative management for ischemic conditions could result in necrosis, prolonged postoperative management, and mortality.

Of relevance, additional studies have reported clinical outcomes such as mortality, complications, and increased use of health care resources associated with delays in surgical intervention [12]. In a recent cohort study evaluating patients with perforated peptic ulcers, every hour of delay from admission to surgery was associated with an adjusted 2.4% decreased probability of survival compared with the previous hour [13]. Conditions such as cholecystitis progressing to perforation, or ischemic consequences for small bowel obstruction are additional examples of surgical delay leading to clinical deterioration and requirements for more extensive operative management. Patients taking FXa inhibitors may experience delays in orthopedic procedures such as hip fracture repair, a procedure in which delay is proven to have adverse

clinical consequences [14]. While there is some variability (at least partially procedure-dependent) in the magnitude of delay associated with increased morbidity and mortality, it is generally accepted that the delay itself meaningfully increases the risk of a negative outcome.

If delaying the surgery is not an option, as is expected for most urgent surgeries, intraoperative management of bleeding complications may consist of hemodynamic support (e.g., fluid/volume replacement, RBC transfusion), use of hemostatic agents (e.g., tranexamic acid) and/or administration of coagulation factor products such as fresh frozen plasma (FFP)/platelet concentrates, recombinant factor VIIa (rfVIIa), factor eight inhibitor bypassing activity, and 3- and 4-factor prothrombin complex concentrates (PCCs) [15]. In general, published guidelines do not recommend the use of nonspecific agents such as PCC for preventative use in the absence of bleeding [16-18].

Though these agents (particularly PCCs) have not been approved by any regulatory agency for use in patients taking FXa inhibitors, they have nevertheless become used as a de facto standard of care for uncontrolled bleeding in patients treated with FXa inhibitors. That said, there is little mechanistic evidence supporting the use of PCCs as reversal agents for FXa inhibitors in any clinical context, including urgent surgery [19]. What clinical evidence exists consists primarily of healthy volunteer studies demonstrating increases in thrombin generation (albeit delayed), and inconclusive data on clinical readouts [20, 21]. Three case series have been published in patients treated with FXa inhibitors who were given PCCs prior to emergent/urgent surgery [22-24], but these were confounded by low numbers ([25], [10], and [24], respectively), poorly (or no) defined criteria for hemostatic efficacy, and relatively little (or no) effort to control for the time from last FXa inhibitor dose. Furthermore, high short-term mortality rates were also reported (29% and 51%, respectively). Taken together, the results cited above indicate that there is little to no evidence supporting the use of nonspecific coagulation factor products for prophylactic use to mitigate bleeding risk in FXa inhibitor-treated patients in need of urgent surgery.

Because of the inadequacy of the two therapeutic strategies discussed above (i.e., delaying surgery or non-specific coagulation factor replacement therapies), an unmet medical need remains for a specific, rapid reversal agent for patients in this clinical scenario. Andexanet has the potential to fill this unmet need.

3.4.3. Rationale for the Dose Regimen

All patients will receive 1 of 2 doses of andexanet based on the specific anticoagulant taken and timing of the last dose.

The andexanet dosing regimens to be examined in this study are as follows:

- Low dose: 400 mg IV bolus at a rate of 30 mg/min (duration of approximately 15 minutes) followed by a continuous infusion at a target rate of 4 mg/min for 120 minutes irrespective of the duration of surgery.

- High dose: 800 mg IV bolus at a rate of 30 mg/min (duration of approximately 30 minutes) followed by a continuous infusion at a target rate of 8 mg/min for 120 minutes irrespective of the duration of surgery.

Extended infusion at the low-dose (4 mg/min) may be administered for up to an additional 4 hours after initial dosing (bolus + infusion) is completed (1) in order to ensure mandatory continuous infusion from start to end of surgery, and (2) may continue into the immediate post-operative coverage per investigator discretion. Total dosing time (initial bolus + initial 120-minute infusion + any extended infusion) should be less than 6.5 hours.

Evidence to support this dosing regimen comes from PK/PD modeling that included results from the ANNEXA-4 study in bleeding patients. Data from the Phase 3 studies with apixaban and rivaroxaban, as well as a recently completed Phase 1 study of Generation 2 andexanet in healthy volunteers (Study 16-512-Direct Inhibitors; Section 1.4.3), confirm the levels of FXa inhibition and recovery of TG observed in the Phase 2 study. These doses of andexanet correspond to decreases in anti-fXa activity that correlate with normalization of hemostasis as measured by a TG assay. The change to the lower dose (400 mg) at 8 hours after the last administered FXa inhibitor dose was based on the PK-PD model that predicted the time at which equivalent anti-fXa activity reversal and TG normalization would be achieved.

In addition to the above, the doses for this study (19-515) were shown to substantially reduce anti-fXa activity and increase TG in a Phase 3b/4 study in which andexanet was given to patients receiving an FXa inhibitor who had acute major bleeding (ANNEXA-4).

3.4.4. Rationale for Extended Infusion or Re-Dosing of Andexanet

In this study, there is potential for patients to require additional andexanet treatment beyond what is initially stipulated (bolus + 120-minute infusion). For example, unpredictable events during surgery may prolong the duration of surgery. Based on clinical judgement of procedural or patient factors, the treating physician may determine that the infusion should additionally extend to the immediate postoperative period. In addition, a surgical patient may bleed after completion of surgery. Therefore, extended andexanet infusions (to address longer surgeries) and re-dosing of andexanet (for post-surgical bleeding events) will be implemented in the protocol.

A low-dose continuous infusion (4 mg/min) for up to an additional 4 hours was selected as the regimen to use for extended infusions, whereas a low-dose bolus (400 mg) plus continuous infusion (4 mg/min for 120 minutes) will be used for re-dosing. The rationale for these dosing levels is based on the premise that the amount of reversal agent required to neutralize an FXa inhibitor diminishes as the inhibitor is eliminated over time.

Investigators will be required to document in the electronic case report form (eCRF) the clinical justification for why subjects require extended infusion of andexanet or additional dosing of andexanet during surgery. Please refer to [Appendix A](#) for the timing of extended infusion or re-dosing of andexanet in surgical patients. The decision criteria for extended duration of dosing or re-dosing during surgery are outlined in Section [6.2](#).

3.4.4.1. *Re-dosing Criteria*

Factors that may determine if re-dosing is appropriate include the treating surgeon's consideration of patient factors, such as degree of visible bleeding, hemodynamic stability, need for hemostatic support products, or to avoid reoperation to control bleeding. The Investigator may also consider clinical suspicion that the patient has levels of FXa inhibition sufficient to contribute to bleeding based on patient factors such as time from last FXa inhibitor dose, safety assessments required by the protocol or routine care and renal function. Additionally, the need for re-operation to control bleeding may be considered reason re-dose to avoid the additional procedure.

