a. Initial Bolus must be completed prior to start of surgery (initial skin incision). b. Initial dosing (bolus + 120 min infusion) should be completely administered regardless of surgery length. c. Infusion should continue throughout the duration of surgery, (defined as skin incision to skin closure or equivalent milestone).				
Criteria for Extended Infusion				
Extended Infusion (4 mg/min only) may continue up to an additional 4 hours to ensure continuous intraoperative infusion for the duration of surgery. The infusion may also continue through the immediate postoperative period at the Investigator's discretion.				

Criteria for Re-Dosing with Andexanet

Consider re-dosing with andexanet (400 mg bolus + 4 mg/min infusion for 120 min) only if:

- a. New, clinically significant, surgery-related, post-operative bleeding occurs after initial course of andexanet (primary bolus + infusion and extended dosing, as applicable) is completed, AND
- b. The treating physician has clinical suspicion that the patient still has levels of FXa inhibition sufficient to contribute to the bleeding, AND
- c. Re-dosing initiation occurs within 12 hours after the completion of the surgical procedure.

FXa = Activated factor X; IV = Intravenous.

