7.2.2. Blood Products

To maintain uniformity in transfusion practices across study participants, it is strongly suggested that the trigger for PRBC transfusion is hemoglobin ≤ 8.0 g/dL (± 1 g/dL). The hemoglobin triggering a transfusion, clinical stability factors (e.g., shock) influencing the decision to transfuse, as well as the number of units transfused should be recorded on the eCRFs.

Whole blood and platelet transfusions may be administered according to standard institutional/local practices and/or guidelines. Investigators may consider using pro-coagulant factor infusions (e.g., 3- or 4-factor PCC/activated PCC, rfVIIa, plasma, FFP) per their judgement in case of hemodynamic necessity. Otherwise, treatment with the above products is strongly discouraged, though not prohibited, during the entire 30-day observation period.

Use of procoagulant factor infusions (e.g., 3- or 4-factor PCC/activated PCC, rfVIIa, plasma, FFP) and whole blood intraoperatively will result in the patient being considered having poor hemostatic efficacy (see [Table 3](#)) with andexanet.

Use of blood products, including number of units transfused and the date and time of administration should be recorded on the eCRFs.

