8.3. Intraoperative Rescue Strategies

Regarding the intraoperative period, it is mandated that andexanet therapy will continue through the duration of the surgical procedure. If a procedure runs longer than the initial bolus and infusion dose of andexanet, the infusion should continue at a low rate (4 mg/min) until the conclusion of the surgery. No additional dosing of andexanet, such as a re-bolus, will be allowed during the procedure, even if bleeding should continue or recur (Section 6.2).

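### Section 3.4.4 refers to re-dosing during surgery and Section 3.4.4.1 lists looser re-dosing factors, while Table 2 confines re-dosing to the post-operative period and Section 8.3 bars it during the procedure

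*Protocol*

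**What the plan says.** Four places in the protocol speak to andexanet given beyond the initial course and the continued infusion.

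- **Section 3.4.4 (rationale).** The opening paragraph gives the purpose: "re-dosing of andexanet (for post-surgical bleeding events) will be implemented in the protocol". Two later sentences move the setting into the operation. Investigators must document in the eCRF "the clinical justification for why subjects require extended infusion of andexanet or additional dosing of andexanet during surgery", and the reader is told that "The decision criteria for extended duration of dosing or re-dosing during surgery are outlined in Section" 6.2.
- **Section 3.4.4.1 (headed as re-dosing criteria).** It lists factors that may bear on the decision: visible bleeding, hemodynamic stability, need for hemostatic products, suspected residual FXa inhibition and avoidance of re-operation. On the last it adds that "the need for re-operation to control bleeding may be considered reason re-dose to avoid the additional procedure".
- **Section 6.2, Table 2.** Re-dosing is to be considered only if three conditions joined by AND are met. The first is "New, clinically significant, surgery-related, post-operative bleeding occurs after initial course of andexanet". The second is clinical suspicion that remaining FXa inhibition contributes to the bleeding. The third is a start no later than 12 hours after the operation ends.
- **Section 8.3 (intraoperative rescue).** The infusion continues at the low rate until surgery ends, and "No additional dosing of andexanet, such as a re-bolus, will be allowed during the procedure, even if bleeding should continue or recur".

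**The concern.** An investigator facing a bleeding patient in the operating room should find one answer on whether more study drug may be given. Section 3.4.4 lists additional dosing during surgery as something distinct from extended infusion, to be justified in the eCRF, and says that criteria for it exist. Section 8.3 says that it is not allowed. Table 2, to which Section 3.4.4 sends the reader, covers only the post-operative patient.

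The second ambiguity concerns the grounds. Section 3.4.4.1 has the title of a criteria list but neither the only-if rule nor the time limit of Table 2. A site could take a factor named there as sufficient on its own.

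At stake are consistent administration of study drug across about 80 sites, exposure of patients to drug that another section prohibits, and clear data on whether the initial dose was adequate. The synopsis and Section 3.1 name adequacy and duration of dosing as information meant to inform a later Phase 3 trial.

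**Working it through.** The check is mainly a comparison of texts.

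**Step 1: may andexanet beyond the continued infusion be given between incision and closure?**

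| Place | What it implies |
|---|---|
| 3.4.4, opening paragraph | Re-dosing is for bleeding after surgery |
| 3.4.4, eCRF sentence | Additional dosing during surgery occurs and needs justification |
| 3.4.4, cross-reference | Criteria for re-dosing during surgery stand in 6.2 |
| 6.2 and Table 2 | Post-operative criteria only |
| 7.3 | Re-dosing as rescue for post-surgical bleeding |
| 8.3 | No, including when bleeding continues or recurs |

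The cross-reference in 3.4.4 points to criteria that do not exist, and its eCRF sentence presupposes an act that 8.3 forbids. Section 7.3 contains parallel sentences on eCRF justification and on the criteria in 6.2, but without any mention of surgery being under way. The amendment overview lists Section 8.3 as an addition of Amendment 2, while the Amendment 1 text already carries the during-surgery sentences. The likely explanation is that the ban was added without revising 3.4.4.

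**Step 2: on what grounds is re-dosing considered?**

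| Feature | Table 2 | 3.4.4.1 |
|---|---|---|
| Logical form | Only if (a) AND (b) AND (c) | Factors that may be considered |
| Bleeding | New, clinically significant, surgery-related, post-operative | Degree of visible bleeding, no threshold |
| Residual FXa inhibition | Required | May also be considered |
| Time limit | 12 hours after the operation | None |
| Avoiding re-operation | Not named | Named as a possible reason |

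The factors in 3.4.4.1 can be read as informing conditions (a) and (b), but the section does not say so.

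**Step 3: amount of drug in the course as written.** The re-dose in 6.2 is 400 mg + 4 mg/min × 120 min = 880 mg. The initial courses are 400 + 480 = 880 mg (low) and 800 + 960 = 1,760 mg (high). A full re-dose is therefore 880/880 = 100% of a low course or 880/1,760 = 50% of a high one. This describes the post-operative course. During surgery an infusion is already running, so it is not established that the whole 880 mg would be extra there.

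**Step 4: does any sample-size figure depend on this?** With n = 80 and p = 0.5, the half-width is 1.96 × √(0.5 × 0.5 / 80) = 0.1096, or 10.96%, which agrees with the stated margin below 11%. And 80/(1 − 0.20) = 100 matches the planned enrollment. Neither figure changes with the re-dosing wording.

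**The case against.** The best defence is that Section 3.4.4 authorises nothing. It is a rationale section, it ties re-dosing to post-surgical bleeding, and it sends the reader to 6.2, where no permission for an intraoperative re-bolus is found. Section 8.3 is explicit. On this view the words about surgery are a leftover, and 3.4.4.1 merely illustrates the judgement needed under Table 2. Much of this stands: a re-bolus during surgery would breach 8.3, and 3.4.4 does not clearly license one. The leftover words still contradict the ban, and nothing in 3.4.4.1 subordinates its list to Table 2.

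A reader might go further and infer that a failing case could be rescued by an intraoperative re-bolus and then counted as a success, biasing the single-arm rate upward. Section 7.2.2 might seem to support this, since "Use of procoagulant factor infusions (e.g., 3- or 4-factor PCC/activated PCC, rfVIIa, plasma, FFP) and whole blood intraoperatively will result" in a poor rating and andexanet is not named. The documents do not support that inference:

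- Section 11.5.1 rates hemostasis over the whole operation, so the bleed that prompted the re-bolus falls inside the rated period.
- Table 3 gives controllable bleeding as its example of Moderate, which Section 11.5.2.1 counts as ineffective.
- The EAC must confirm the rating.
- Under Section 7.3, EAC-confirmed post-surgical bleeding is already poor, however treated.
- The list in 7.2.2 is given as examples, so silence on andexanet does not show that it is exempt.

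It is true that no explicit rule classifies an intraoperative re-bolus, and a rating of Good after mild bleeding cannot be excluded. But that is a missing rule for an act that 8.3 already forbids. One case among 80 is 1/80 = 1.25 percentage points. That is simple division, not an estimate of bias, because the documents give no expected number of cases.

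**Conclusion.** The concern holds as an internal contradiction. Section 3.4.4 conflicts with Section 8.3 and Table 2 on whether andexanet beyond the continued infusion may be given during the operation. Section 3.4.4.1 leaves its relation to Table 2's joined conditions and 12-hour limit unstated. It should be corrected because it concerns when patients receive study drug.

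Its size is two sentences in 3.4.4 and one short subsection. No bias in the primary proportion is shown or quantified, and no planned number is wrong. The conclusion rests on the Amendment 2 text as available. The stated changes in the Japan amendments and the two administrative letters do not address these sections. The EAC Charter and the statistical analysis plan were not available, and either may say how additional intraoperative andexanet is handled.

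**What to change.** Reconcile Sections 3.4.4 and 3.4.4.1 with Table 2 and Section 8.3 so that one rule applies throughout:

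1. Make the eCRF sentence and the cross-reference in 3.4.4 agree with 8.3 and 6.2 on whether anything beyond the continued infusion may be given between incision and closure.
2. State in 3.4.4.1 how its factors relate to Table 2's three joined conditions and 12-hour limit.

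Which clinical rule stands is the sponsor's decision. Whether to add an endpoint rule for re-boluses given in breach of the ban can also be left to the sponsor; this point does not require one. The cost is wording only, with no change to sample size, endpoint definitions or analysis.
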